4.1.3 Selection of doses in the trial

For the SRD part, oral doses in the range of 2 mg to 800 mg have been selected in order to assess the safety and tolerability of BI 730357 in healthy male volunteers, and to investigate the PK of [REDACTED]. The selected doses cover a safe starting dose in the sub-therapeutic range, the estimated therapeutic range and potentially supra-therapeutic doses within the levels determined by toxicological investigations (see Section 1.2).

The intra-individual comparisons of the BA part investigating the relative bioavailability of tablet fasted versus tablet fed and of tablet fasted versus oral solution fasted are planned to be conducted with a dose of 25 mg as it is assumed that this dose covers the therapeutic range and might be used in the subsequent clinical development.

4.1.4 Drug assignment and administration of doses for each subject

The treatments to be evaluated are outlined in Tables 4.1.4: 1 (SRD part) and [4.1.4: 2](#) (BA part) below. The number of units / dose volume for placebo corresponds to the number of units / dose volume of the respective dose level.

Table 4.1.4: 1 BI 730357 and placebo treatments for the SRD part

Dose group	Fasting condition predose	Substance	Pharmaceutical form	Unit strength	Number of units /dose volume per administration	Total dose
1	fasted	BI 730357	oral solution	1 mg/mL	2 mL	2 mg
2	fasted	BI 730357	oral solution	1 mg/mL	8 mL	8 mg
3	fasted	BI 730357	film-coated tablet	25 mg	1 tablet	25 mg
4	fasted	BI 730357	Film-coated tablet	50 mg	1 tablet	50 mg
5	fasted	BI 730357	Film-coated tablet	50 mg	2 tablets	100 mg
6	fasted	BI 730357	Film-coated tablet	50 mg	4 tablets	200 mg
7	fasted	BI 730357	Film-coated tablet	50 mg	8 tablets	400 mg
8	fed ¹	BI 730357	Film-coated tablet	50 mg	8 tablets	400 mg
9	fed ²	BI 730357	Film-coated tablet	50 mg	8 tablets	400 mg
10	fed ²	BI 730357	Film-coated tablet	50 mg	16 tablets	800 mg
1-2	fasted	Placebo*	oral solution	--	identical to active treatment	--
3-7	fasted	Placebo*	Film-coated tablet	--	identical to active treatment	--
8-10	fed	Placebo*	Film-coated tablet	--	identical to active treatment	--

* Subjects receiving placebo are equally distributed across dose groups

1 Drug administration after a standard continental breakfast

2 Drug administration after a standard high-fat breakfast

3 Identical to active treatment

Proprietary confidential information © 2017 Boehringer Ingelheim International GmbH or one or more of its affiliated companies

Table 4.1.4: 2

BI 730357 film-tablets and oral solution for the BA part

Treatment	Substance	Pharmaceutical form	Unit strength	Number of units / dose volume per administration	Total Dose
T1 (oral solution fasted)	BI 730357	oral solution	10 mg/mL	2.5 mL	25 mg
T2 (tablet fed)	BI 730357	Film-coated tablet	25 mg	1 tablet	25 mg
R (tablet fasted)	BI 730357	Film-coated tablet	25 mg	1 tablet	25 mg

The oral solutions for dosing will be prepared according to the reconstitution instruction given in Appendix [10.1](#) under the responsibility of the Investigator. The Investigator can decide at any time to discontinue dosing or to decrease the dose escalation by adding intermediate doses in case of intolerance or due to safety concerns.

The trial medication will be administered to the subjects, while in a sitting or standing position, as an oral dose together with about 240 mL of water under supervision of the investigating physician or an authorised designee in the morning of Day 1. The so-called four-eye principle (two-person rule) should be applied for administration of trial medication and – if applicable – its preparation (e.g. reconstitution), if correct dosage cannot be ensured otherwise. Administration will be performed following an overnight fast, which is to start no later than 10 h before the scheduled dosing.

In treatment T2 (tablet fed) of the BA part and dose groups 9 (400 mg BI 730357 or placebo) and 10 (800 mg BI 730357 or placebo) of the SRD part, a high-fat, high-calorie breakfast will be served 30 min before drug administration. In dose group 8 (400 mg BI 730357 or placebo) of the SRD part, a standard continental (normal-fat, normal-calorie) breakfast will be served 30 min before drug administration. The test meals must be completely consumed prior to drug administration. The composition of the standard high-fat, high-calorie breakfast will be in compliance with the FDA guidance ‘Food-Effect Bioavailability and Fed Bioequivalence Studies’ [[R03-2269](#)] as detailed in Table 4.1.4: 3. The composition of the standard continental breakfast will be detailed in [Table 4.1.4: 4](#).

Table 4.1.4: 3

Composition of the high-fat, high-calorie meal

Ingredients	kcal
Sum ¹	984

¹ The total caloric content was supplied approximately as following: 150 kcal as protein, 250 kcal as carbohydrate, and 500 to 600 kcal as fat.

Table 4.1.4: 4

Composition of the continental breakfast

Ingredients	kcal
Sum ¹	458

¹ The total caloric content was supplied approximately as following: 88 kcal as protein, 133 kcal as carbohydrate, and 237 kcal as fat.

Subjects will be kept under close medical surveillance until at least 24 h following drug administration. During the first 6 hours after drug administration subjects of the SRD part will be confined to bed with a bed inclination angle of at least 45 degrees unless lower or supine positioning is required for trial-related measurements (e.g. recording of 12-lead ECG). During the first 4 hours after drug administration subjects of the BA part will only be allowed to lie down if supine positioning is required for trial-related measurements (e.g. recording of 12-lead ECG). For restrictions with regard to diet see Section [4.2.2.2](#).

4.1.5 Blinding and procedures for unblinding

4.1.5.1 Blinding

In the present trial, treatments of the SRD part will be blinded to subjects only. With the rising dose design, single-blind conditions regarding the subjects' treatment (active or placebo) are maintained within each dose group, however the current dose level will be known to subjects and Investigators. Treatments of the BA part will be open-label.

The database of this trial will be handled open-label, because no bias with regard to data cleaning of safety measures is expected. This is considered acceptable because the potential for bias seems to be low and does not outweigh practical considerations. The bioanalyst will be blinded for the BA part only.

The bioanalyst of analytical laboratory and the trial pharmacokineticist may receive the randomisation codes of the SRD part prior to official unblinding to perform the preliminary PK analysis. He or she will treat the codes confidentially.

In addition, the drug metabolism scientist may receive the randomisation codes prior to official unblinding to perform metabolites in safety testing analysis (MIST). He or she will confirm in writing that the codes will be treated confidentially.

Within the ECG laboratory, the staff involved with interval measurements and assessments will be blinded with respect to the treatment within each dose level and also with regard to the recording date and time as well as time the points of the ECGs. The interval measurements for a given subject will be performed in a random and blinded sequence by a single technician. No more than two different blinded readers will evaluate the ECGs of the study.

Proprietary confidential information © 2017 Boehringer Ingelheim International GmbH or one or more of its affiliated companies

4.1.5.2 Procedures for emergency unblinding

As this trial will be conducted single-blinded (SRD part) or open-label (BA part), the treatment information will be known. Therefore, no emergency envelopes will be provided.

4.1.6 Packaging, labelling, and re-supply

Drug supplies will be provided by the Department of Pharmaceutical Development of Boehringer Ingelheim Pharma GmbH & Co. KG, Biberach, Germany.

The clinical trial supply consists of containers holding the trial medication which are labelled with trial identification. The required information according to the German Drug Law as well as Annex 13/EU GMP Guideline will be provided on the containers. Smaller boxes and/or bottles within the clinical trial supply containers will be labelled with:

- BI trial number
- Name of product and strengths or identification code
- Pharmaceutical dosage form, quantity of dosage units
- Route and mode of administration
- Term 'For Clinical Trial Use' (domestic language)
- Sponsor name and address
- Storage conditions
- Use-by date
- Subject or medication number
- Batch number
- Visit number (BA part only)

The telephone number of the Sponsor and name, address and telephone number of the trial site are given in the subject information form. The EudraCT number is indicated on the title page of this protocol as well as on the subject information and informed consent forms. Examples of the labels will be available in the ISF.

No re-supply is planned.

4.1.7 Storage conditions

Drug supplies will be kept in their original packaging and in a secure limited access storage area according to the recommended (labelled) storage conditions. Where necessary, a temperature log must be maintained to make certain that the drug supplies are stored at the correct temperature. If the storage conditions are found to be outside the specified range, the local clinical monitor (as provided in the list of contacts) is to be immediately contacted.

4.1.8 Drug accountability

The Investigator will receive the investigational drugs delivered by the Sponsor when the following requirements are fulfilled:

- Approval of the trial protocol by the IRB / ethics committee

Proprietary confidential information © 2017 Boehringer Ingelheim International GmbH or one or more of its affiliated companies

- Approval/notification of the regulatory authority, e.g. competent authority
- Availability of the curriculum vitae of the principal Investigator
- Availability of a signed and dated clinical trial protocol

Only authorised personnel as documented in the form 'Trial Staff List' may dispense medication to trial subjects. The trial medication must be administered in the manner specified in the CTP. All unused medication will be disposed locally by the trial site upon written authorisation by the clinical monitor. Receipt, usage and disposal must be documented on the respective forms. Account must be given for any discrepancies.

The Investigator must maintain records of the product's delivery to the trial site, the inventory at the site, the use by each subject, and the disposal of unused products.

These records will include dates, quantities, batch / serial numbers, expiry ('use-by') dates, and the unique code numbers assigned to the investigational products and trial subjects. The Investigator will maintain records that document adequately that the subjects were provided the doses specified by the CTP, and that reconcile all investigational products received from the Sponsor. At the time of disposal, the Investigator must verify that all unused or partially used drug supplies have been returned by the clinical trial subject and that no remaining supplies are in the Investigator's possession.

4.2 OTHER TREATMENTS, EMERGENCY PROCEDURES, RESTRICTIONS

4.2.1 Other treatments and emergency procedures

There are no special emergency procedures to be followed. No additional treatment is planned. However, in case of adverse events in need of treatment, the Investigator can authorise symptomatic therapy. In those cases, subjects will be treated as necessary and, if required, kept under supervision at the trial site or transferred to a hospital until all medical evaluation results have returned to an acceptable level.

4.2.2 Restrictions

4.2.2.1 Restrictions regarding concomitant treatment

In principle, no concomitant therapy is allowed. All concomitant or rescue therapies will be recorded (including time of intake on study days) on the appropriate pages of the CRF.

4.2.2.2 Restrictions on diet and life style

While admitted to the trial site the subjects are restricted from consuming any other foods or drinks than those provided by the staff. Standardised meals will be served at the time points described in the [Flow Chart](#). No food is allowed for at least 4 h after drug intake.

From 1 h before drug intake until lunch, fluid intake (except for the beverages served with the breakfast in the SRD or BA part) is restricted to the water administered with the drug, and an additional 240 mL of water served at 2 h and 4 h post-dose (mandatory for all subjects). From lunch until discharge from the study centre, liquid intake is restricted to additional 3 litres.

Proprietary confidential information © 2017 Boehringer Ingelheim International GmbH or one or more of its affiliated companies

During the days of urine collection, subjects will be advised to drink at least 1.5 litres per day.

Alcoholic beverages, grapefruits, Seville oranges (sour or bitter oranges) and their juices, and dietary supplements and products containing St. John's wort (*Hypericum perforatum*) are not permitted starting 4 days before the first administration of trial medication until after the last PK sample of each study period is collected.

Smoking is not allowed during in-house confinement at the trial site.

Methylxanthine-containing drinks or foods (such as coffee, tea, cola, energy drinks, and chocolate) are not allowed from 10 h before until 24 h after administration of trial medication.

Excessive physical activity (such as competitive sport) should be avoided starting 7 days before the first administration of trial medication until the end of trial examination.

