* Only one treatment period (Visit 2) for dose groups 1-7 and 10. Two identical treatment periods separated by a wash-out phase of at least 14 days between drug administration for dose group (DG) 8 (Visit 2) and DG 9 (Visit 3). In DGs 8-9 the same subjects will be included.

1. Subject must be informed and written informed consent obtained prior to starting any screening procedures. Screening procedures include physical examination, check of vital signs, ECG (including rhythm strip of at least 15 minutes), safety laboratory (including drug screening), demographics (including determination of body height and weight, smoking status and alcohol history), relevant medical history, concomitant therapy and review of inclusion/exclusion criteria. Pharmacogenetic samples will be collected if needed.
2. The time is approximate; the respective procedure is to be performed and completed within 3 h prior to drug administration. Allocation to treatment may be performed at any time following enrolment but must be completed prior to (first) drug administration.
3. If several actions are indicated at the same time point, the intake of meals will be the last action.
4. End of trial examination includes physical examination, vital signs, ECG, safety laboratory, recording of AEs and concomitant therapies.
5. Only urine drug screening and alcohol breath test will be done at this time point.
6. AEs and concomitant therapies will be recorded throughout the trial, but will be specifically asked for at the time points indicated in the Flow Chart above.

Proprietary confidential information © 2017 Boehringer Ingelheim International GmbH or one or more of its affiliated companies

7. Safety laboratory to be taken and to be medically evaluated within 3 days prior to administration of study drug; this ambulatory visit including the safety laboratory can be omitted, if the screening examination is performed on Days -3, -2 or -1.
8. Two blood sample for stability testing will be taken at this time point (refer to Section [5.5.2.4](#))
9. The ECG recording has to be performed as triple at this time point
10. Sampling times and periods may be adapted based on information obtained during the trial (e.g. preliminary PK data) including addition of samples and visits as long as the total blood volume taken does not exceed 500 mL per subject
11. Including blood sample for metabolite identification (refer to Section [5.5.2.2](#))

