12. A blank urine sample (x) is to be obtained prior to administration of trial medication. Other urine samples are to be collected over the stated post-dose intervals (◀—|—|→) 0-4, 4-8, 8-12, 12-24 and 24-48 h.
13. Two blood samples should be collected: 4.3 mL in sodium citrate tubes and 4.5 mL in lithium heparin tubes.
14. The ECG will be recorded as single ECG at this time point
15. Only haematology, automatic WBC differential and lymphocytes subtypes (refer to Table [5.2.3: 1](#)) at this time point
16. Standard continental breakfast (see Table [4.1.4: 3](#)) in DG 8 and standard high-fat breakfast (see Table [4.1.4: 4](#)) in DGs 9 and 10

Proprietary confidential information © 2017 Boehringer Ingelheim International GmbH or one or more of its affiliated companies

FLOW CHART FOR THE BIOAVAILABILITY PART

Visit	Day	Planned time (relative to drug administration [h:min])	Approximate clock time of actual day [h:min]	Event and comment	Safety laboratory	PK blood ⁸	12-lead ECG	Vital signs (BP, PR)	Questioning for AEs and concomitant therapy ⁶
1	-21 to -1			Screening (SCR) ¹	x		x ¹⁰	x	
2/3/4*	-3 to -1	-72:00 ⁷	08:00	Ambulatory visit	x				x
1	1	-2:00	06:00	Admission to trial site in visits 2-4, allocation to treatment in visit 2 only ²	x ^{2,5}	x ²	x ^{10,2}	x ²	x ²
		-0:30	07:30	Standard breakfast ⁹					
		0:00	08:00	Drug administration					
		0:30	08:30		x				
		1:00	09:00		x				x
		1:30	09:30		x				
		2:00	10:00	240 mL fluid intake	x	x ¹⁰	x	x	
		2:30	10:30		x				
		3:00	11:00		x				
		4:00	12:00	240 mL fluid intake, thereafter lunch ³	x	x ¹⁰	x	x	
		5:00	13:00		x				
		6:00	14:00		x	x ¹⁰	x	x	
		8:00	16:00	Snack (voluntary) ³	x				x
		10:00	18:00	Dinner ³	x	x ¹⁰	x		
		12:00	20:00		x				x
2	2	24:00	08:00	Breakfast (voluntary) ³ , discharge from trial site	x	x	x ¹⁰	x	x
		34:00	18:00	Ambulatory visit		x			x
		48:00	08:00	Ambulatory visit	x	x ¹⁰	x	x	
3	3	72:00	08:00	Ambulatory visit	x				x
		96:00	08:00	Ambulatory visit	x				x
4	4	168:00	08:00	Ambulatory visit	x ¹¹	x			x
		9 to 13		End of trial (EOT) examination ⁴	x		x ¹⁰	x	x

* Three identical treatment periods separated by wash-out phases of at least 8 days between each drug administration

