7.5.2 Secondary endpoints

Assessment of dose proportionality (SRD part, tablet application under fasting conditions)

Dose proportionality of the PK endpoints $AUC_{0-\infty}$ and C_{max} in plasma of BI 730357 tablets under fasting conditions (dose groups C, D, E, F, and G) will be explored as a secondary analysis using the power model that describes the functional relationship between dose and PK endpoints. The basic model consists of a regression model applied to log-transformed data under fasting conditions. The corresponding ANCOVA (Analysis of Covariance) model includes the logarithm of the dose as a covariate.

The model is described by the following equation:

CTP:

$$Y_{ij} = \alpha + \beta * X_i + \varepsilon_{ij}$$

where

Y_{ij} logarithm of the pharmacokinetic endpoint for subject j at dose level i ;
where $i = 1, 2, \dots, 5$ $j = 1, 2, \dots, 6$,
 α intercept parameter;
 β slope parameter;
 X_i logarithm of dose i ;
 ε_{ij} random error associated with subject j at dose level i (assumed to be independent and identically normally distributed).

This equation can be fit as a linear regression model. Based on the estimate for slope parameter (β), a 2-sided 95% CI for the slope will be computed. Perfect dose proportionality would correspond to a slope of 1. The assumption of a linear relationship between the log-transformed pharmacokinetic endpoint and the log-transformed dose will be checked.

If dose proportionality over the entire dose range under fasting conditions investigated cannot be shown, an attempt will be made to identify dose range(s), where dose proportionality can be assumed.

This analysis will be accomplished by using the XPKISTAT macro (design DB), based on the PKS.

Intra-individual comparison of fed conditions (SRD part, DG 8 and 9 only)

The intra-individual comparison of fed conditions is primarily to be determined on the basis of the parameters $AUC_{0-\infty}$ and C_{max} . Those parameters will be ln-transformed (natural logarithm) prior to fitting the model.

The statistical model used for the analysis of $AUC_{0-\infty}$ and C_{max} will be an ANOVA (analysis of variance) model on the logarithmic scale. This model will include effects accounting for the following sources of variation: 'subjects' and 'treatment'. The effect 'subjects' will be considered as random, whereas the 'treatment' effect will be considered as fixed. The model is described by the following equation

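### The ban on alcohol, grapefruit, Seville orange and St. John's wort has no stated restart before later doses: DG 9 gets no lead-in, and BA doses 2 and 3 at best a partial one

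*Protocol*

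**What the plan says.** Protocol Section 4.2.2.2 prohibits alcohol, grapefruit, Seville orange, their juices and St. John's wort products "starting 4 days before the first administration of trial medication until after the last PK sample of each study period". The start is tied to the first dose only, the end to each period.

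Two sets of subjects are dosed more than once:

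- **DG 8 and DG 9.** The note to the SRD flow chart describes "Two identical treatment periods separated by a wash-out phase of at least 14 days between drug administration", with DG 8 at Visit 2 and DG 9 at Visit 3. The note then makes clear that nobody new enters for the second of these: "In DGs 8-9 the same subjects will be included". Section 6.2.2 fixes the order: continental breakfast first, high-fat breakfast second.
- **BA part.** The note to its flow chart reads: "Three identical treatment periods separated by wash-out phases of at least 8 days between each drug administration".

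Neither spacing has a maximum. In both flow charts the last scheduled PK blood sample is at 168 h.

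SAP Section 7.5.2 analyses DG 9 against DG 8 on the log scale with subject and treatment as the only effects. The BA model also has sequence and period effects.

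**The concern.** Both within-subject comparisons assume that a subject's periods differ only in the planned treatment, and the flow charts call the periods identical. The sponsor judged that these products should be excluded for 4 days before dosing. As written, that protection is complete only before the first dose.

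The problem is specific to this sentence. In the same section, the methylxanthine rule is set around administration in general (10 h before to 24 h after), so it applies to every dose. The rule on strenuous activity starts before the first dose but runs unbroken to the end-of-trial examination.

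DG 9 is the main worry. It is always the second period and always the high-fat period, so a carry-in effect of a restricted product cannot be told apart from the effect of the meal. A period term would not help, because with one fixed order period and diet coincide.

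The wording also weakens detection. Intake that the text permits is not a protocol deviation, so it need not reach the listings described in SAP Section 6.2 or be weighed when the PK set is decided.

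**Working it through.** **Inputs**

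- Lead-in before the first dose: 4 days (Section 4.2.2.2).
- Last scheduled PK sample: 168 h = 7 days after dosing (both flow charts).
- Minimum dose spacing: 14 days = 336 h (DG 8 to DG 9); 8 days = 192 h (BA).
- Sampling tolerance from 72 h onwards: ±70 min (Section 6.1).
- Active subjects in DG 8/9: 6, with no replacement (Sections 3.1 and 3.3.5).

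The documents give no figure of their own to reproduce here.

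**Gap and remaining coverage**

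Gap = dose spacing − 7 days. Lead-in days still covered by the previous period's ban = max(0, 4 − gap).

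| Step | Spacing (days) | Gap (days) | Covered of 4 days |
|---|---|---|---|
| DG 8 to DG 9 | 14 (minimum) | 7 | 0 |
| BA, doses 2 and 3 | 8 (minimum) | 1 | 3 |
| BA, doses 2 and 3 | 9 | 2 | 2 |
| BA, doses 2 and 3 | 10 | 3 | 1 |
| BA, doses 2 and 3 | 11 or more | 4 or more | 0 |

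A 168 h sample taken 70 min late changes little: 192 − 168 − 1.17 = 22.8 h (BA) and 336 − 168 − 1.17 = 166.8 h (DG 9).

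**Does another rule close the gap?**

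- In-house diet control starts with admission, about 2 h before dosing.
- The overnight fast (Section 4.1.4) starts no later than 10 h before dosing. If it is taken to exclude juice and alcohol as well as food, it shortens the open time to 168 − 10 = 158 h (DG 9) and 24 − 10 = 14 h (BA at minimum spacing).
- The breath test before each treatment (Section 5.2.3) is a spot check for recent alcohol.
- The urine drug screen (Table 5.2.3: 2) lists none of these products.
- The rule against concomitant therapy (Section 4.2.2.1) may reach St. John's wort, but not grapefruit, Seville orange or alcohol.

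**Illustration of leverage in DG 8/9**

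If one of 6 active subjects has DG 9 exposure multiplied by f, the geometric mean ratio is multiplied by f^(1/6). The values of f are assumed:

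- f = 1.5: 1.5^(1/6) = 1.070, or +7%
- f = 2: 2^(1/6) = 1.122, or +12%
- f = 0.5: 0.5^(1/6) = 0.891, or −11%

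**The case against.** **The sentence could mean one unbroken ban.** It can be read as running from 4 days before the first dose until the last PK sample of every period has been taken. The breath test before each treatment, which exists to support the alcohol restrictions, presupposes some restriction before later doses. This reading is possible, but the text does not state it, and a subject told that the ban ends with each period's last sample would not infer it. What stands is that the wording is ambiguous; a lapse in practice is not proven.

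**A reader might infer that BA periods 2 and 3 have no lead-in at all.** The documents do not support that. At the 8-day minimum the previous period's ban still covers 3 of the 4 days. All six sequences are used and period is in the model, so a systematic difference between the first and later periods is largely absorbed. The rationale for global amendment 3 already reports a fed-versus-fasted result, so BA data were available by then and rewording chiefly affects DG 8/9.

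**Other rules give partial cover.** Concomitant therapy is asked about at the visit on Days -3 to -1, PK values may be excluded for restricted medication, and SAP Table 6.2: 1 has codes for prohibited medication and improper washout. This helps for St. John's wort. It does not reach the food and drink items.

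**The effect is hypothetical and the PK analysis is exploratory.** Both are true. No acceptance range is set and the primary endpoint is adverse reactions. This limits the weight of the point but does not remove the confounding in DG 8/9.

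**Conclusion.** The point holds, mainly for DG 9. On the natural reading of Section 4.2.2.2, at least 7 days outside the ban come immediately before that dose and none of the 4 lead-in days is covered. The comparison has a fixed order and about 6 active subjects, so a resulting change in exposure would be reported as an effect of the high-fat meal.

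In the BA part the gap is at least the last 24 h before doses 2 and 3. Coverage is 3 of 4 days at the minimum spacing and falls to none at 11 days or more. The likely cost there is added within-subject variability rather than bias.

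This rests on the last PK sample staying at 168 h (the flow charts allow sampling times to be adapted) and on the restriction being applied as worded. A reader might go further and conclude that the high-fat/continental ratio is biased by some 7% to 12%. That does not follow: the documents give neither the sensitivity of BI 730357 to these products nor an expected intake, and those figures only show how much one subject can move the ratio. It is a cheap correction that should be made, not a flaw that invalidates the comparison.

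**What to change.** Reconcile the reference to the first administration with the reference to each study period, so that the same pre-dose restriction applies before every dose. Either tie the lead-in to each administration, or state one unbroken ban up to the last PK sample of the last period. DG 8/9 is the priority. Compliance can be asked about at the visit already scheduled on Days -3 to -1 of each period.

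For periods run under the present wording, list any known intake between periods for review at the report planning and database lock meeting, so that its relevance to the PK set is decided openly.

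The cost is one phrase in the protocol and the subject instructions, with no new visits or samples. Subjects keep the restriction somewhat longer. For DG 8/9 this is 4 extra days with a lead-in tied to each dose, or at least 7 with an unbroken ban. For the BA part at minimum spacing it is 1 extra day before each of doses 2 and 3 under either option.
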